**Table 8: Guidelines for Interruption and Restarting of Study Treatment**

Adverse Event	Value or Grade	Recommendation
Grade 3/4 neutropenia judged to be related to study drugs	ANC decreases to $< 1.0 \times 10^9/L$ for at least 7 days OR ANC decreases to $< 1.0 \times 10^9/L$ with an associated body temperature $\geq 38.5^{\circ}C$ ( $101.3^{\circ}F$ ) OR ANC decreases to $< 0.5 \times 10^9/L$	Interrupt tafasitamab and parsaclisib dosing. Follow CBC every 7 days. Growth factors (eg, G-CSF) and antimicrobial prophylaxis are to be used, as per local guidelines.
	ANC returns to $\geq 1.0 \times 10^9/L$	Provided all other criteria are fulfilled, resume dosing of tafasitamab and/or parsaclisib at the same dose. Monitor as clinically indicated.
Grade 2-4 thrombocytopenia judged to be related to study drugs	Platelet count decreases to $< 75 \times 10^9/L$	Interrupt tafasitamab and parsaclisib dosing. Follow CBC every 7 days.
	Platelet count decreases to $\geq 75 \times 10^9/L$	Provided all other criteria are fulfilled, resume dosing of tafasitamab and/or parsaclisib at the same dose. Monitor as clinically indicated.
Other clinically significant toxicities judged to be related to study drugs	Grade 3	Interrupt the administration of the study drug(s) to which the toxicity is judged to be related to up to 28 days until the toxicity has resolved to $\leq$ Grade 1.
	Toxicities resolve to $\leq$ Grade 1	Restart tafasitamab and parsaclisib at the same doses. If assessed as related to parsaclisib, restart at the next lower dose of parsaclisib (see Table 11). Monitor as clinically indicated.
	Recurrent Grade 3 after 2 dose reductions of parsaclisib	Discontinue tafasitamab and parsaclisib administration and follow-up per Protocol. Exceptions require approval of sponsor.
	Grade 4	Discontinue tafasitamab and parsaclisib administration and follow-up per Protocol. Exceptions require approval of sponsor.

CBC = complete blood count.

Note: If, based on medical judgment, the treating physician considers a laboratory parameter change or AE not to be a study drug-related toxicity, but to represent a natural fluctuation in or progression of the underlying disease, then it is at the physician's discretion and assessment of the individual risk/benefit ratio to determine whether the participant should be dosed. The decision and rationale behind the decision should be documented in the source data.

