### **6.2.1.3. Administration**

### **6.2.2. Parsaclisib**

Participants will self-administer parsaclisib as an oral treatment. Parsaclisib will be administered as 20 mg QD for 8 weeks followed by 2.5 mg QD.

Parsaclisib should be taken at approximately the same time each day.

Administration of parsaclisib will be calendar-based. Delays or interruptions in study treatment will not affect the dosing schedule of parsaclisib; 20 mg QD will be administered only during the first 8 weeks (Days 1-56); all participants will switch to 2.5 mg QD on Day 57.

Treatment with parsaclisib will continue until a criterion is met for treatment discontinuation.

Parsaclisib will be administered in the study clinic on days when blood samples are collected for PK as indicated in Table 3 and Section [8.4](#).

See [Appendix F](#) for instructions to participants for handling parsaclisib.

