**Table 11: Dose Levels for Parsaclisib**

	Dose, C1D1 to C2D28 (Day 1 to Day 56)	Dose, C3D1 to EOT (Day 57 to EOT)
Starting dose	20 mg QD	2.5 mg QD
First dose reduction	10 mg QD	1 mg QD
Second dose reduction	5 mg QD	Not applicable

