**Table 12: Dose Modifications for Parsaclisib for Diarrhea/Colitis**

Parsaclisib Current Dose	Dose Modification
≥ 2.5 mg QD	20 mg QW
1 mg QD	20 mg QW or 10 mg QW
20 or 10 mg QW	Restart next lower dose 10 mg QW or 5 mg QW
5 mg QW	Permanently discontinue

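### A participant first dose-reduced on or after Day 57 cannot meet the Table 8 trigger of two parsaclisib reductions, because Table 11 lists only one reduction in that period

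*Protocol*

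**What the plan says.** Protocol Table 8 has a residual row for clinically significant drug-related toxicities other than the cytopenias. At Grade 3, dosing is interrupted until recovery. For the restart it says: "If assessed as related to parsaclisib, restart at the next lower dose of parsaclisib (see Table 11". Both drugs are stopped on "Recurrent Grade 3 after 2 dose reductions of parsaclisib", and exceptions need sponsor approval. The row names no dosing period and gives no counting convention.

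Table 11 has one column for Days 1 to 56 and one for Day 57 to end of treatment. Its reduction rows read "First dose reduction 10 mg QD 1 mg QD" and "Second dose reduction 5 mg QD Not applicable". The starting doses above them are 20 mg QD and 2.5 mg QD.

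Section 6.2.2 makes parsaclisib dosing calendar-based: "all participants will switch to 2.5 mg QD on Day 57". It does not mention participants already reduced, or the reduction count.

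Table 12 gives a once-weekly ladder for diarrhea/colitis that ends in "Permanently discontinue". Section 6.6.2.2 names both Table 11 and Table 12 as sources of reduction levels, but Table 8 refers only to Table 11.

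**The concern.** The stopping rule counts to two on a ladder that, from Day 57, has one rung. A site with a participant at the lowest Table 11 level and a recurrent Grade 3 event would find no lower dose to restart at and no met condition for stopping. The silence on earlier reductions adds a second problem: two sites could treat the same dosing history differently and both be following the text.

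This bears first on participant safety. Late toxicity is anticipated, since the protocol justifies the lower dose after Week 8 partly by the wish to limit late-onset adverse events. It also bears on reporting. Tolerability is a Phase 1b primary objective, and SAP Section 8.2.4 tabulates parsaclisib reductions and discontinuations due to TEAEs. Those counts would partly reflect how sites read the tables.

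**Working it through.** No sample size or error rate is involved. The check counts levels and follows each possible path.

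**Inputs**
- Reductions required by the Table 8 recurrence row: 2.
- Table 11, Days 1 to 56: 20, 10 and 5 mg QD, so 3 − 1 = 2 reductions.
- Table 11, Day 57 on: 2.5 and 1 mg QD, so 2 − 1 = 1 reduction.
- Section 6.2.2: all participants move to 2.5 mg QD on Day 57.

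**Step 1: levels against the trigger.** Before Day 57, 2 levels meet the required 2. From Day 57, 1 level falls short of 2 by one.

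**Step 2: paths.** Let *a* be the reductions before Day 57 (0 to 2) and *b* those from Day 57 (0 or 1). The counting rule is unstated, so three readings are tried:
- A: everyone moves to 2.5 mg QD, and the count is *a* + *b*.
- B: a reduced level carries across Day 57, and the count is *a* + *b*. Then *b* = 1 is possible only if *a* = 0.
- C: everyone moves to 2.5 mg QD, and the count restarts, so it equals *b*.

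| *a* | *b* | Count, A | Count, B | Count, C |
|---|---|---|---|---|
| 0 | 0 | 0 | 0 | 0 |
| 0 | 1 | 1 | 1 | 1 |
| 1 | 0 | 1 | 1 | 0 |
| 1 | 1 | 2 (met) | no such path | 1 |
| 2 | 0 | 2 (met) | 2 (met) | 0 |
| 2 | 1 | 3 (met) | no such path | 1 |

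**Step 3: dead ends.** A dead end has no lower Table 11 level left and a trigger that is not met.
- The path 0 + 1 is a dead end under all three readings. Under A it is the only one.
- Under B, 1 + 0 is also a dead end, because the participant enters Day 57 already at the lowest level.
- Under C, every path with *b* = 1 is a dead end.

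**Step 4: same history, different action.** Take two reductions before Day 57, then a recurrent Grade 3 event on 2.5 mg QD. Under A the count is 2 and both drugs stop. Under C the count is 0 and parsaclisib restarts at the next level.

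**Step 5: Table 12.** From 2.5 mg QD the diarrhea/colitis ladder runs through 20, 10 and 5 mg QW, which is 3 steps before permanent discontinuation. Nothing says whether these steps count toward the 2 in Table 8.

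**The case against.** The case on the other side has weight. Table 8 does not confine the count to one dosing period. Section 6.2.2, read literally, fixes the Day 57 dose for everyone, so only the count is left open. Section 6.6.2 calls the Table 8 modifications general guidance, to be applied with clinical judgment and the medical monitor. Grade 4 toxicity has its own stopping row. Table 10 has specific rules for several toxicities, including stops for recurrent diarrhea/colitis. Sections 6.6.3 and 7.1.1 require discontinuation for unacceptable toxicity. DLTs are confined to Cycle 1, before Day 57, and the SAP tables count actions taken, with no formal test.

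Most of this limits the point without removing it. The recurrence row requires sponsor approval for exceptions, so sites must be able to tell when it applies. Section 6.6.3 rests on judgment or on a delay of more than 14 days, and neither is a rule for recurrence after a reduction.

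Three stronger readings are tempting, and the documents do not support them:
- A reader might infer that the rule cannot operate for anyone from Day 57. That follows only if the count restarts, which no passage says. Under reading A three paths still meet it.
- A reader might infer that Grade 3 toxicity after Day 57 has neither a restart level nor any ground for stopping. A first such event on 2.5 mg QD does have a listed lower level, and unacceptable toxicity remains a separate ground.
- A reader might divide 56 days by the estimated 24 months to get a share of time affected. That estimate is of participation and includes screening and follow-up. A share of days also does not measure how many participants are affected.

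**Conclusion.** The point holds in a limited form. For a participant first reduced on or after Day 57, Tables 8 and 11 conflict: a recurrent Grade 3 event has no lower level and cannot meet the stopping trigger, whichever counting rule is used. For participants reduced earlier, the outcome depends on a convention that the protocol does not state. This is an inconsistency between a stated stopping rule and its own dose table. It should be corrected, though it does not threaten the dose-confirmation decision or the ORR analysis.

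The size is one missing level against a requirement of two. A participant treated for more than 112 days (2 × 56) spends over half of that treatment in the one-reduction period. The number who would meet the dead end cannot be estimated, because no rate of recurrent Grade 3 toxicity after a late reduction is given.

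Two assumptions are made. Reductions in Table 8 are taken to be steps down Table 11, the only table it cites. The scheduled Day 57 change is not counted as a reduction, since Table 11 labels 2.5 mg QD a starting dose.

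**What to change.** Reconcile the Table 8 recurrence row with Tables 11 and 12 and Section 6.2.2, so that the trigger can be met in both dosing periods. State explicitly:
- whether reductions before Day 57 count after the switch;
- whether Table 12 steps count toward the two.

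Which levels or stopping criteria apply is a clinical decision for the sponsor, and none is proposed here. The cost is protocol amendment wording and a note to sites. No SAP method, sample size or data collection needs to change.

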### 6.6.2.1. Tafasitamab Dose Modifications for Cytokine Release Syndrome and Infusion-Related Reactions

Dose reductions of tafasitamab are not permitted. Drug interruptions or discontinuation may occur in the case of severe IRRs, allergic reactions, infections, febrile neutropenia, or severe hematologic toxicity. Delaying the tafasitamab dose is permitted for no more than 2 days (eg, if dosing was planned on Day 8, delaying that dose is allowed up to Day 10). Alternatively, an infusion of tafasitamab may be skipped completely, and the next scheduled dose will be administered (eg, if an infusion is skipped on Day 8, the next dose will be administered on Day 15). In the event tafasitamab administration is interrupted due to toxicity, other regularly scheduled assessments should still be performed.

Some mAb treatments in NHL have been associated with Grade 3 IRRs during the first infusion in participants. These IRRs have been ameliorated or eliminated by fractionating the dose into 2 infusions separated by at least 24 hours. If the full dose of tafasitamab cannot be administered in 1 day, the dose may be split into a second administration that must be given on the subsequent day. After the occurrence of a first-dose Grade 3 IRR, the next 3 infusions for this participant will be split: one-third of the dose administered on the original schedule followed by the remaining two-thirds on the next day, with each infusion administered over 2 hours. If there are no IRRs with the 3 consecutive split infusions, then the investigator can consider reverting to a single 2-hour infusion for the subsequent infusions.

Infusion-related reactions have commonly been reported for participants with CLL or NHL treated with tafasitamab. Infusion-related reaction will be defined according to the NCI CTCAE v5.0 definition of IRR and CRS. [Table 9](#) provides guidance for the management of IRRs by grade.

**Table 9: Management of Infusion-Related Reactions/Cytokine Release Syndrome**

IRR Grade	CRS Grade	Interventions
2	1	
The infusion should be stopped immediately.
 
The participant should receive appropriate treatment with an antihistamine and/or acetaminophen or methylprednisolone (or equivalent) as clinically indicated.
 
Once the symptoms have been resolved or reduced to Grade 1 (IRR only) according to investigator assessment, the infusion can be continued at an infusion rate of 50% of the speed so far. If, after 1 hour, the participant's symptoms do not return and vital signs are stable, the infusion rate may be increased every 30 minutes, as tolerated, to the baseline rate.
 
If a participant who developed a Grade 2 IRR or Grade 1 CRS receives further infusions of tafasitamab, then premedication should be given before all subsequent infusions of tafasitamab throughout the study.

**Table 9: Management of Infusion-Related Reactions/Cytokine Release Syndrome (Continued)**

IRR Grade	CRS Grade	Interventions
3	2	
The infusion should be stopped immediately.
 
The participant must receive appropriate treatment with an antihistamine and/or acetaminophen or methylprednisolone (or equivalent) and, if necessary, further medications (ie, epinephrine, bronchodilator).
 
After the complete resolution of all symptoms, and after having received appropriate prophylactic medication(s) as described above, the infusion may be resumed at an infusion rate of 25% of the speed so far. If, after 1 hour, the participant's symptoms do not return and vital signs are stable, the infusion rate may be increased to a maximum of 50% of the baseline speed.
 
If, after the resumption of the infusion, symptoms return (irrespective of grade), the infusion must be stopped immediately and the infusion tubing should be disconnected from the participant. Based on the investigator's decision, the participant may receive further tafasitamab provided clinically appropriate precautions were undertaken.
 
If a participant who developed a Grade 3 IRR or Grade 2 CRS receives further infusions, then premedication should be given before all subsequent infusions of tafasitamab throughout the study.
 
If precluded from further tafasitamab administrations, the participant may continue treatment with parsaclisib.

4	3 or 4	
The infusion should be stopped immediately and the infusion tubing should be disconnected from the participant.
 
The participant must receive appropriate treatment with an antihistamine and/or acetaminophen or methylprednisolone (or equivalent) and, if necessary, further medications (ie, epinephrine, bronchodilator).
 
The participant must not receive any further tafasitamab infusions but may continue treatment with parsaclisib as per protocol.

#### 6.6.2.2. Dose Modifications for Parsaclisib

Dose modification guidance for AEs that have been previously observed in participants receiving parsaclisib or are potential class-effect AEs are provided in [Table 10](#).

The starting dose and dose reduction levels of parsaclisib are provided in [Table 11](#) and [Table 12](#).

**Table 10: Toxicity Management Guidelines for Parsaclisib**

Adverse Event	Recommendation
Chemistry	
AST and/or ALT is Grade 3 ( $> 5.0 \times \text{ULN}$ ). Note: In participants with liver metastasis-related elevations at baseline, contact sponsor to discuss clinical management.	Step 1: Interrupt both tafasitamab and parsaclisib. Monitor weekly until the toxicity has resolved to $\leq$ Grade 1 ( $< 3.0 \times \text{ULN}$ ). Step 2: Restart tafasitamab at the same dose and parsaclisib at next lower dose with medical monitor approval. Monitor as clinically indicated.
Other toxicities	
Diarrhea (Grade 1)	Step 1: Treat with antimotility agents (eg, 2 mg loperamide followed by 2 mg every 4 hours or after every unformed stool) and initiate supportive care. Monitor approximately every 48 hours until resolved. If not improved after 48 hours, treat per guidance for Grade 2.
Diarrhea (Grade 2)	Step 1: Interrupt tafasitamab and parsaclisib. Perform workup for infection (including CMV, Clostridium difficile , etc) immediately. Initiate or continue supportive care. Monitor approximately every 48 hours until resolution. Step 2: If improved within 48 hours and/or infection* is confirmed, restart tafasitamab and parsaclisib at the same schedule and dose after resolved to $\leq$ Grade 1 and continue to monitor. *For infectious diarrhea/colitis, follow institutional standard of care guidelines and restart parsaclisib according to clinical judgment after resolved to $\leq$ Grade 1. Consult with medical monitor if needed. Step 3: If not improved within 48 hours and infection is ruled out, start oral steroids, or consider IV steroids if participant is being given IV fluids. If no improvement with oral steroids, switch to IV steroids. Step 4: When diarrhea resolves to $\leq$ Grade 1, continue supportive care and taper steroids according to institutional standards of care. When taper is complete (eg, no steroid or $\leq 10 \text{ mg/day}$ prednisolone or equivalent) and diarrhea is $\leq$ Grade 1, restart parsaclisib at the next lower dose with approval of the medical monitor. Step 5: If Grade 2 diarrhea reoccurs, treat per guidance for diarrhea ( $\geq$ Grade 3)/noninfectious colitis. Step 6: If $\geq$ Grade 2 diarrhea reoccurs a third time, permanently discontinue parsaclisib.

**Table 10: Toxicity Management Guidelines for Parsaclisib (Continued)**

Adverse Event	Recommendation
Diarrhea ( $\geq$ Grade 3) Noninfectious colitis (any grade; confirmed or suspected)	
Step 1: Interrupt tafasitamab and parsaclisib. Perform workup for infection (including CMV, C. difficile, etc) immediately. Initiate or continue supportive care. Consider colonoscopy with biopsy for diarrhea <math>\geq</math> Grade 3 and/or if symptomsa are suggestive of colitis. Monitor every 48 hours until resolution.
 
Step 2: If infection* is ruled out, start oral steroids, or consider IV steroids if participant is being given IV fluids. If no improvement with oral steroids within 48 hours, switch to IV steroids.
 
*For infectious diarrhea/colitis, follow institutional standard of care guidelines and restart parsaclisib according to clinical judgment after resolved to <math>\leq</math> Grade 1. Consult with medical monitor if needed.
 
Step 3: When diarrhea/colitis resolves to <math>\leq</math> Grade 1, continue supportive care and taper steroids according to institutional standards of care. When taper is complete (eg, no steroid or <math>\leq</math> 10 mg/day prednisolone or equivalent) and diarrhea/colitis is <math>\leq</math> Grade 1, restart tafasitamab and parsaclisib as described herein and with approval of the medical monitor. Continue to monitor.
 
Step 4: If <math>\geq</math> Grade 3 diarrhea/colitis (any grade) reoccurs, permanently discontinue parsaclisib.

Pneumonitis (Grade 1)	
Step 1: Interrupt tafasitamab and parsaclisib until the toxicity has resolved.
 
Step 2: Restart tafasitamab at the same dose and parsaclisib at next lower dose. Monitor as clinically indicated.

Pneumonitis ( $\geq$ Grade 2)	Permanently discontinue tafasitamab and parsaclisib.
Skin toxicity (eg, rash, pruritus, etc, unless otherwise specified) (Grade 2-3)	
Step 1: Interrupt tafasitamab and parsaclisib until the toxicity has resolved to <math>\leq</math> Grade 1.
 
Step 2: Restart tafasitamab and parsaclisib at the same dose. If assessed as related to parsaclisib, restart at the next lower dose.

Exfoliative dermatitis (Grade 1)	
Step 1: Interrupt tafasitamab and parsaclisib until the toxicity has resolved.
 
Step 2: Restart tafasitamab at the same dose and parsaclisib at the next lower dose. Monitor as clinically indicated.

Exfoliative dermatitis ( $\geq$ Grade 2)	Permanently discontinue tafasitamab and parsaclisib.
Intestinal perforation (any grade)	Permanently discontinue tafasitamab and parsaclisib.
PJP infection	Interrupt tafasitamab and parsaclisib. Permanently discontinue tafasitamab and parsaclisib if PJP infection is confirmed.

**Table 10: Toxicity Management Guidelines for Parsaclisib (Continued)**

Adverse Event	Recommendation
CMV infection	Participants with CMV viremia without associated clinical signs of CMV infection should be carefully monitored. Consider interrupting tafasitamab and parsaclisib for participants with CMV viremia and clinical signs of infection until the infection has resolved. Restart tafasitamab at the same dose and parsaclisib reduced by 1 dose level if approved by the medical monitor.
Varicella zoster infection	Interrupt tafasitamab and parsaclisib. Restart tafasitamab and/or parsaclisib only by approval of the medical monitor.
Any Grade 1 or Grade 2 toxicity unless otherwise specified	Continue tafasitamab and parsaclisib. Treat the toxicity; monitor as clinically indicated.

a Diarrhea accompanied by abdominal pain and/or mucus or blood in stool.

**Table 11: Dose Levels for Parsaclisib**

	Dose, C1D1 to C2D28 (Day 1 to Day 56)	Dose, C3D1 to EOT (Day 57 to EOT)
Starting dose	20 mg QD	2.5 mg QD
First dose reduction	10 mg QD	1 mg QD
Second dose reduction	5 mg QD	Not applicable

### 6.6.2.3. Supportive Care Guidelines for Diarrhea/Colitis

Participants should be instructed to immediately report any event of diarrhea, irrespective of grade. Treatment with parsaclisib may be modified according to the guidelines in [Table 12](#) to allow for resolution of diarrhea/colitis.

Participants should receive appropriate supportive care measures as deemed necessary by the investigator. For any  $\geq$  Grade 1 diarrhea, participants should be advised to drink liberal quantities of clear fluids. If sufficient oral fluid intake is not feasible, fluid and electrolytes should be substituted via IV infusion. Participants should try to eat 5 to 6 small meals per day; low-fat, high-protein foods; and cooked instead of raw vegetables. Participants may supplement their diet with bananas, rice, applesauce, and toast to reduce the number of bowel movements and may also try crackers, gelatin, noodles, or oatmeal. Participants should avoid fried, fatty, greasy, or spicy foods; milk, milk products, and acidic drinks; high-fiber foods and foods that cause gas; and alcohol, caffeine, and herbal supplements.

For each occurrence, attempts should be made to rule out other causes, such as metastatic disease or bacterial or viral infections (including CMV), which might require additional supportive care.

It may be necessary to perform additional procedures, such as colonoscopy with biopsy, as part of evaluation of the event. Note that several courses of steroid tapering may be necessary because symptoms may worsen when the steroid dose is decreased. Any procedure performed must be captured in the appropriate eCRF.

Participants should be carefully monitored for signs and symptoms of enterocolitis (such as diarrhea, abdominal pain or cramping, blood or mucus in stool, with or without fever) and of bowel perforation (such as peritoneal signs and ileus).

